Principal-Investigator:

Dr. med. dent. [name]

Signature

Clinical Study Protocol - Clinical evaluation of a new dual cure universal adhesive (Adhese Universal DC) in the indirect restorative therapy: A randomised, controlled clinical trial

(ClinO, Appendix 3, 1.1, 2.1, 3.1, 4.1; Appendix 5, 2b)

Sponsor / Sponsor-Investigator	Ivoclar Vivadent AG
Study Title:	Clinical evaluation of a new dual cure universal adhesive (Adhese Universal DC) in the indirect restorative therapy: A randomised, controlled clinical trial
Short Title / Study ID:	Clinical evaluation of Adhese Universal DC in the indirect restorative therapy / LL3615088
Protocol Version and Date:	03 10.03.2021
Trial registration:	Registry of the U.S. National Library of Medicine (http://www.clinicaltrials.gov): NCT04475679. Supplementary federal database (Portal for clinical trials in Switzerland - SNCTP, https://www.kofam.ch/en/snctp-portal/): SNCTP000004028. As soon as the new electronic system EUDAMED is operational, the clinical investigation will be retrospectively registered.
Study category and Rationale	Category A According to Article 20 Categorisation of clinical trials of medical devices this clinical trial is a category A clinical trial since a medical device that has conformity marking will be used and the medical device will be used according to its instruction for use.
Clinical Phase:	n.a
Background and Rationale:	A post market clinical follow up study (PMCF) with Adhese Universal DC is planned to ensure the safety and efficacy of the product. It is a study with two arms. Inlays and onlays for molars and premolars will be luted with Adhese Universal DC or Adhese Universal.
Objective(s):	The null hypothesis is that there is a statistically significant difference between control and test group with respect to postoperative hypersensitivity. The secondary objective of this study is to assess the long-term clinical efficacy of the tested material when compared to the control in terms of marginal quality and retention/fracture rate of the restorations and vitality and fracture rate of treated teeth.
Outcome(s):	The primary endpoint of this RCT is the incidence rate of postoperative hypersensitivity. The secondary outcomes are the vitality and fracture rate of restored teeth and the retention/fracture rate of restorations.
Study design:	Randomised, control clinical trial – Equivalence study

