Inclusion / Exclusion criteria:	The participants are aged between 18-65 years. The teeth included in the study show an indication for inlays/ onlays (defective restoration or decay), are vital, with healthy periodontium, and contact with at least one adjacent tooth and with an opposing tooth. Excluded from the study will be pregnant women, participants with known allergies to the used materials and/or local anaesthetics, participants with severe general diseases, participants with bad oral hygiene and high caries activity. Participants who suffer from symptoms of a SARS-CoV2 infection.
Measurements and procedures:	After information and written informed consent the participants will receive a dental treatment in relation to the restorative indication (caries, tooth/restoration fracture, insufficient restoration etc), which means that the inlay/ onlay cavity will be prepared and a digital impression with an intraoral scanner (Trios 3Shape) will be taken. Then, the cavities will be temporarily restored with provisional restorations. The scans and impressions will be sent to the lab where dental technicians will provide the final restorations made of lithium disilicate e.max CAD. In the following appointment the final restorations will be luted and final corrections as well as the finishing and polishing procedures will be done. The baseline recall will take place 7-10 days after the insertion of the restoration. At the baseline recall the study specific parameters will be evaluated according to the FDI Criteria ranging from 1 excellent to 5 clinically not acceptable. The recalls will be performed at 6, 12, 24, 36 and 60 months.

Clinical Study Protocol - Clinical evaluation of a new dual cure universal adhesive (Adhese Universal DC) in the indirect restorative therapy: A randomised, controlled clinical trial

Study Product / Intervention:	Indirect restorations are bonded to the tooth surface by a dental adhesive. Dental adhesives can be light cured or dual cured. The latest generation of adhesives are universal adhesives. Additionally, a composite luting cement is used to fill the gap between tooth and restoration and to bond the restoration to the adhesive layer as well as the restoration. In the test group of the RCT Adhese Universal DC will be used in conjunction with the luting cement Variolink Esthetic. Adhese Universal DC is a new, universal, dual curing adhesive.

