Control Intervention (if applicable):	In the control group Adhese Universal will be used in conjunction with the luting cement Variolink Esthetic. Adhese Universal is a universal, light curing adhesive which has been on the market for 6 years and has proven its clinical efficacy and safety.
Number of Participants with Rationale:	80 Teeth: 40 in the study group and 40 in the control group, at maximum two teeth per participant.
Study Duration:	6 years
Study Schedule:	September 2020 December 2026
Investigator(s):	[name], [name], Tel. [REDACTED] E-Mail: [REDACTED] [name], [name], Tel. [REDACTED] E-Mail: [REDACTED] [name], [name], Tel. [REDACTED] E-Mail: [REDACTED] [name], [name], Tel. [REDACTED] E-Mail: [REDACTED] [name], [name], Tel. [REDACTED] E-Mail: [REDACTED]
Study Centre(s):	This RCT is a single centre study.
Statistical Considerations:	Non-parametric test (Mann-Whitney) between control and study group p=0.1 will be applied regarding the clinical parameters evaluated in this study. The sample was calculated using the G*power Software 3.1.9.7.
GCP Statement:	This study will be conducted in compliance with the protocol, the current version of the Declaration of Helsinki, the ICH-GCP or ISO EN 14155 as well as all national legal and regulatory requirements.

ABBREVIATIONS

Provide a list of abbreviations used on the protocol - to be completed

AE	Adverse Event
BASEC	Business Administration System for Ethical Committees, (https://submissions.swissethics.ch/en/)
CA	Competent Authority (e.g. Swissmedic)
CEC	Competent Ethics Committee
ClinO	Ordinance on Clinical Trials in Human Research (in German: KlinV, in French: OClin, in Italian: OSRUM)
eCRF	Electronic Case Report Form
CTCAE	Common terminology criteria for adverse events
DSUR	Development safety update report
GCP	Good Clinical Practice
IB	Investigator's Brochure
Ho	Null hypothesis
H1	Alternative hypothesis
HRA	Federal Act on Research involving Human Beings (in German: HFG, in French: LRH, in Italian: LRUM)
IMP	Investigational Medicinal Product
IIT	Investigator-initiated Trial
ISO	International Organisation for Standardisation
ITT	Intention to treat
MD	Medical Device
MedDO	Medical Device Ordinance (in German: MepV, in French: ODim)
PI	Principal Investigator
SDV	Source Data Verification
SOP	Standard Operating Procedure
SPC	Summary of product characteristics

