SUSAR	Suspected Unexpected Serious Adverse Reaction
TMF	Trial Master File

STUDY SCHEDULE

(SPIRIT #13; ICH E6 6.4.2)

Study Periods	Screening	Treatment, Intervention Period		Follow-up					
Visit	1	2	3	4	5	6	7	8	9
Time (hour, day, week)	-60 days	2 hours	2 hours	7-10d	6 mon	12 mon	24 mon	36 mon	60 mon
Patient Information and Informed Consent	x								
Medical History	x								
In- /Exclusion Criteria	x								
Tooth Examination	x								
Pregnancy Test (only in case of uncertainty)	x								
Randomisation			x						
Vitality test	x	x		x	x	x	x	x	x
VAS for tooth sensitivity		x		x	x	x*	x*	x*	x*
Preparation of tooth, impression and cementation of provisional restoration		x							
Try-in and cementation of final restoration			x						
Use of Adhese Universal DC or Adhese Universal			x						
Primary Variables				x	x	x	x	x	x
Secondary Variables				x	x	x	x	x	x
Adverse events			x	x	x	x	x	x	x

x*: only for participants who suffer from any kind of postoperative hypersensitivity

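### The one stated test treats up to two teeth per participant as independent, so it does not hold its 10% level, and the primary endpoint has no stated period or case definition

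*Combined protocol and SAP*

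**What the plan says.** The text available for review is the synopsis, the abbreviation list and the study schedule. Five places bear on this point.

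- **Statistical Considerations (synopsis):** "Non-parametric test (Mann-Whitney) between control and study group p=0.1 will be applied regarding the clinical parameters evaluated in this study". No other analysis is described. Sidedness is not given, and nothing is said about teeth from the same mouth.
- **Number of Participants (synopsis):** 80 teeth, 40 per group, with up to two from one participant. The text does not say how many participants will contribute two, or whether both teeth would go to the same arm.
- **Outcome(s) and Study design (synopsis):** "The primary endpoint of this RCT is the incidence rate of postoperative hypersensitivity", in a trial described as "Randomised, control clinical trial – Equivalence study". The endpoint has no visit, no period and no definition of a case.
- **Measurements and procedures (synopsis):** "At the baseline recall the study specific parameters will be evaluated according to the FDI Criteria", and "The recalls will be performed at 6, 12, 24, 36 and 60 months".
- **Study Schedule (table):** the row "Primary Variables" is marked at visits 4 to 9, from the 7-10 day recall to month 60, which makes six occasions. The secondary-variable row carries the same marks. A separate row, "VAS for tooth sensitivity", is starred from month 12, and the footnote restricts it to this group: "only for participants who suffer from any kind of postoperative hypersensitivity".

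**The concern.** There are two gaps, and both affect the primary comparison.

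**Independence.** Two teeth in one mouth share a patient, a pain threshold and a way of reporting symptoms, so their outcomes are likely to be correlated. The Mann-Whitney variance assumes 80 independent observations. If pairs share an arm, that variance is too small and the test rejects too often. If pairs are split between arms, it is too large and the test rejects too rarely. Either way, the stated 10% is not the error of the test as written.

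**Which quantity is tested.** The endpoint is called an incidence, the schedule records it six times, and no rule says whether the decisive figure is cumulative or belongs to one visit. Both a VAS and FDI scores are collected, and neither is named as defining hypersensitivity. Two analysts could both follow the text and test different quantities. In a trial described as an equivalence study, that choice should not remain open once data by arm can be seen.

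**Working it through.** **Inputs from the documents:** 40 teeth per arm, level 0.1, Mann-Whitney test, up to two teeth per participant, six visits.

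**Assumptions (the documents give no figures):** two-sided test; incidence 10% or 20%, equal in both arms; intraclass correlation (ICC) 0.1, 0.3 or 0.5 between two teeth of one participant.

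The sample size cannot be reproduced as a starting point, because the text names the software but gives no power, effect size, rates or margin.

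**Step 1. Formula.** On yes/no data the test is in effect a comparison of two proportions, with critical value 1.645. Let D be the true variance of the difference divided by the variance the test assumes.

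- All teeth in same-arm pairs: D = 1 + ICC
- Half the teeth in same-arm pairs: D = 1 + 0.5 × ICC
- All teeth in pairs split between arms: D = 1 − ICC

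The actual error is 2 × (1 − Φ(1.645/√D)). For example, same-arm pairs with ICC 0.3 give 1.645/√1.3 = 1.443 and an error of 0.149. Split pairs with ICC 0.3 give 1.645/√0.7 = 1.966 and an error of 0.049.

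**Step 2. Results.** The simulation columns use 60,000 trials with the tie-corrected test, shown as incidence 10% / 20%.

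| Arrangement | ICC | Formula | Simulation |
|---|---|---|---|
| All same-arm pairs | 0.1 | 0.117 | 0.124 / 0.119 |
| | 0.3 | 0.149 | 0.159 / 0.155 |
| | 0.5 | 0.179 | 0.198 / 0.184 |
| Half of teeth in same-arm pairs | 0.1 | 0.108 | 0.117 / 0.110 |
| | 0.3 | 0.125 | 0.134 / 0.127 |
| | 0.5 | 0.141 | 0.152 / 0.143 |
| All pairs split between arms | 0.1 | 0.083 | 0.091 / 0.085 |
| | 0.3 | 0.049 | 0.057 / 0.051 |
| | 0.5 | 0.020 | 0.029 / 0.022 |

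With no correlation, the same test has an error of 0.109 at 10% incidence and 0.102 at 20%. The departures therefore come from the pairing and not from ties or small numbers.

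**Step 3. After accounting for participant.** A t test on participant means, with all teeth in same-arm pairs, had an error of 0.096-0.107 over the same settings.

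**Step 4. Power cost if pairs share an arm.** Assume true rates of 10% and 30%. The standard error for independent teeth is √((0.1×0.9 + 0.3×0.7)/40) = 0.0866, and 0.20/0.0866 = 2.309. The plain test's power is about Φ((2.309 − 1.645)/√D). A participant-based test has about Φ(2.309/√D − 1.645).

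| ICC | Plain | Participant-based | Difference |
|---|---|---|---|
| 0.1 | 0.737 | 0.711 | 3 points |
| 0.3 | 0.720 | 0.648 | 7 points |
| 0.5 | 0.706 | 0.595 | 11 points |

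The plain test's advantage here comes from its inflated error.

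**Step 5. Which visit.** This is an illustration under an assumed early difference that fades: 30% against 10% at 7-10 days, 15% against 5% at 6 months, and 5% in both arms later. Teeth are independent, with latent correlation 0.5 between visits. The test is significant in 75% of simulated trials at 7-10 days, 46% at 6 months, about 11% at each later visit, and 55% for cumulative incidence. These are different true quantities, so the spread is not an error of the test. It shows only that the unstated choice can decide the answer. If rates and differences do not change over time, each single visit gives the same chance.

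**The case against.** **Only a summary is available.** A full statistics section could define the period, the case and the handling of paired teeth. This stands as a limit on confidence. If such a section exists, the synopsis needs only to be aligned with it.

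**The clustering effect has no known direction or size.** This is correct. The range of 2% to 20% spans the stated level, and the effect vanishes if nobody contributes two teeth. But the plan expressly allows two, and the stated test is right only if pairs are absent or uncorrelated.

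**The wording already implies a time point.** The word postoperative may suggest the first recall, and incidence may suggest a cumulative count. These readings compete, neither is stated, and the schedule marks primary variables to month 60.

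A reader might also infer four stronger points that the documents do not support:

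- *All six visits are tested and any one can decide, so the false-positive rate is several times 10%.* No such rule is stated, so no any-visit error rate should be attached to this plan.
- *The same test is prescribed for vitality, fracture and retention.* That is one reading of the phrase about clinical parameters. It may equally mean the graded FDI scores, for which a rank test is ordinary.
- *A survival analysis is needed for 60-month failures.* That is a preference, not a correction. A robust Kaplan-Meier comparison also needs a fallback when an arm has no events.
- *The VAS restriction rules out a primary analysis after month 6.* From month 12 the restriction limits comparison of VAS scores. For an incidence, participants without hypersensitivity are simply non-cases.

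**Conclusion.** The concern holds in limited form. In the available text, the only stated test ignores that two teeth may come from one participant, so its error is not the stated 10%. If all teeth are paired, it is about 12-20% when pairs share an arm and about 9% down to 2% when they are split. If half the teeth are in same-arm pairs, it is about 11-15%. These figures rest on an assumed incidence of 10-20%, an assumed ICC of 0.1-0.5 and a two-sided test. The direction cannot be settled, because the allocation of pairs is not stated.

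The figures describe the chance of a false significant difference. The corresponding error for a false claim of equivalence cannot be computed, because the available text gives no margin.

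The missing period and case definition add a second, unquantified freedom: the primary result can depend on the visit or the cumulative measure chosen. The point should be acted on. Confidence is moderate because only the summary sections can be seen.

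**What to change.** 1. **Name one decisive primary analysis.** Use either cumulative incidence over a stated period, with each tooth counted once, or status at one named visit.
2. **Define a case.** State which measure, VAS or FDI score, and which value counts as hypersensitivity.
3. **Account for participant.** State whether both teeth of a participant go to the same arm. Replace the plain test with a participant-level comparison or a participant-robust variance. Specify a participant-level permutation or exact method as fallback when an arm has no or very few events.
4. **Report the other visits as secondary.** Give between-arm differences with confidence intervals and make no confirmatory claim.

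**Cost.** The change concerns the wording of the outcome, statistics and schedule entries, with no new visits or measurements. Version 03 is dated 10.03.2021, after the planned start in September 2020, so an amendment may be needed. It should be settled before results by arm are seen. Later recalls lose confirmatory status for the primary endpoint. If pairs share an arm, power falls by about 3 to 11 points against the plain test in the 10% against 30% example, depending on the ICC. The loss is smaller if few participants contribute two teeth.

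### The trial is labelled an equivalence study, but the only analysis named is a Mann-Whitney difference test at p=0.1 with no margin or interval, so non-significance on the rate outcomes cannot support equivalence

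*Combined protocol and SAP*

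**What the plan says.** All the relevant statements are in the synopsis.

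- Study design: "Randomised, control clinical trial – Equivalence study".
- Objective(s): one formal hypothesis, on the primary endpoint: "The null hypothesis is that there is a statistically significant difference between control and test group with respect to postoperative hypersensitivity". The secondary objective is "to assess the long-term clinical efficacy of the tested material when compared to the control in terms of marginal quality and retention/fracture rate", and it also covers vitality and fracture of the treated teeth.
- Outcome(s): the primary endpoint is an incidence rate (postoperative hypersensitivity). "The secondary outcomes are the vitality and fracture rate of restored teeth and the retention/fracture rate of restorations".
- Measurements and procedures: "the study specific parameters will be evaluated according to the FDI Criteria", a five-grade scale. "The recalls will be performed at 6, 12, 24, 36 and 60 months".
- Number of Participants with Rationale: "80 Teeth: 40 in the study group and 40 in the control group, at maximum two teeth per participant".
- Statistical Considerations: "Non-parametric test (Mann-Whitney) between control and study group p=0.1 will be applied regarding the clinical parameters evaluated in this study". The sample size is attributed to G*Power without its inputs.

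The Study Schedule lists the secondary variables at every visit from the 7-10 day recall to 60 months. No margin, confidence interval, equivalence test or separate method for proportions appears in the synopsis, the abbreviation list or the schedule.

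**The concern.** An equivalence conclusion needs an interval for the difference that lies inside limits set in advance. A Mann-Whitney test asks only whether the data contradict equality. With 40 teeth per arm and few failures, it will often fail to reject when the arms truly differ. Someone reading a 60-month report of no significant difference, in a trial called an equivalence study, could not see how large a difference remains possible. The comparison of long-term efficacy with the control would then go unanswered in the terms the design sets.

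**Working it through.** **Inputs.** From the synopsis: 40 teeth per arm, Mann-Whitney, level 0.1. Assumed, because the text does not give them: a two-sided test, all event counts and rates, yes/no coding of the rate outcomes, independent teeth and no dropout.

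**The plan's own figure.** The 40 per arm cannot be reproduced, because no effect size, power, rate or margin is given. It fits several input sets, using n = 2(z_alpha + z_power)²/d²:

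- d=0.60, two-sided 0.10, 85% power: 2(1.645+1.036)²/0.36 = 39.9, so 40.
- d=0.65, two-sided 0.05, 80% power: 2(1.960+0.842)²/0.4225 = 37.2, so 38. Dividing by 0.955 for Mann-Whitney gives 39.8, so 40.

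The sample size therefore does not reveal an unstated margin.

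**What the test does on yes/no data.** With x1 and x2 events in n=40 per arm, N=80 and pooled rate P=(x1+x2)/80, the tie-corrected statistic (no continuity correction) is z = (x1-x2)/n ÷ sqrt[P(1-P)(2/n)(N/(N-1))].

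- 4/40 vs 1/40: P=0.0625, z = 0.075/0.0545 = 1.377, p=0.169. Pearson chi-square gives 0.166.
- 6/40 vs 2/40: P=0.10, z = 0.10/0.0675 = 1.481, p=0.139. Chi-square gives 0.136.

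On such data it is in effect a chi-square test of difference. It is valid for that purpose, but its output is a p-value.

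**What the p-value leaves open.** 90% Miettinen-Nurminen score intervals for the difference:

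| Events | p | Difference (points) | 90% interval (points) |
|---|---|---|---|
| 4/40 vs 1/40 | 0.17 | +7.5 | -1.8 to +18.5 |
| 6/40 vs 2/40 | 0.14 | +10.0 | -1.2 to +22.3 |
| 0/40 vs 0/40 | undefined | 0 | -6.4 to +6.4 |

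A different method (Newcombe) gives -2.1 to +18.2 for 4 vs 1, so the reading does not depend on the interval chosen.

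In the last row, P=0 makes the statistic 0/0; reporting p=1 would be a convention. The score limit there is k/(40+k) with k = 1.645²×80/79 = 2.740, that is 2.740/42.740 = 6.4 points.

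**How often a real difference gives non-significance.** Exact binomial enumeration over all pairs of counts, 40 per arm, two-sided 0.1:

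| True failure rates | Non-significant |
|---|---|
| 10% vs 5% | 76% |
| 15% vs 5% | 54% |
| 18% vs 6% | 48% |
| 24% vs 8% | 36% |
| 30% vs 10% | 25% |

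A three-fold difference is missed more often than not only when the lower rate is about 5% or less.

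**Two teeth per participant.** If every participant gives two teeth with within-person correlation r, the standard error of the difference is multiplied by sqrt(1+r) when both teeth are in one arm and by sqrt(1-r) when they are in different arms (equal event rates). At an assumed r=0.3 these are 1.14 and 0.84. The correction can go either way, and the available text does not say how a second tooth is allocated.

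**The case against.** The strongest reply is that the documents never commit the error. The text does not say that a non-significant secondary result will be read as equivalence. The equivalence label may belong to the primary endpoint alone, since only hypersensitivity has a stated hypothesis and the secondary objective is simply to assess. That null also says a difference exists, which is the direction of an equivalence null, under which non-significance would not establish equivalence. All of this stands, so it would be wrong to infer that the sponsor plans to declare equivalence from p>0.1. It does not remove the gap. The null is worded by statistical significance, not by a margin, and the one named test cannot reject it. If the label is confined to the primary endpoint, the problem moves to another incidence rate with the same analysis.

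Second, a one-line synopsis entry is not a full statistics section. The statements about what is absent apply only to the synopsis, abbreviation list and schedule; they do not establish that no margin exists elsewhere.

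Third, the phrase clinical parameters may mean only the FDI grades, for which Mann-Whitney is a reasonable difference test. In that case the available text names no analysis for the rates, and the same remedy is needed.

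Two stronger readings should be resisted. Mann-Whitney is not invalid on yes/no data; it only answers a different question. Nor would a tripled failure rate usually be missed: that depends on the underlying rate, as the enumeration shows.

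**Conclusion.** The point holds for the text available. A difference test at 0.1, without a margin or interval, cannot support an equivalence conclusion on the secondary rate outcomes or on the primary incidence rate, and nothing else named in that text could. The size is material at 40 teeth per arm: results that count as non-significant can leave differences of about 18 to 22 points open, and a doubling from 5% to 10% would go undetected in about three trials out of four. These sizes rest on assumed event rates, independent teeth, no dropout and a two-sided test. The logical point does not depend on them. It should be corrected before analysis, but it does not call for a change to the trial's conduct.

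**What to change.** For each outcome stated as a rate:

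1. Report the cumulative 60-month failure proportion per arm, with a failed tooth staying failed, and state how teeth lost to follow-up enter the denominator. For hypersensitivity, use the incidence over its own defined period.
2. Report the between-arm difference with a 90% score-type interval that keeps non-zero width when there are no events, such as Miettinen-Nurminen.
3. State how two teeth from one participant are allocated and account for it accordingly, for example by an effective sample size or a sensitivity analysis with one tooth per participant.
4. If equivalence is claimed, judge the interval against a margin stated in advance. Otherwise label the outcome descriptive and state that p>0.1 is not read as equivalence.

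Kaplan-Meier curves may be added as a supplement for dropout, but the Greenwood interval should not be relied on when an arm has no events, because its width is then zero. Mann-Whitney may stay for the ordinal FDI grades as a test for a difference, with the same statement about non-significance.

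The cost is SAP wording and a little more analysis of data already scheduled for collection, with no change to visits, treatment or sample size. The intervals will be visibly wide.

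### The visit-2 sensitivity VAS precedes randomisation but has no stated analytic use; adjusting score comparisons for it costs little and gains nothing to a modest amount, while incidence should stay unadjusted

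*Combined protocol and SAP*

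**What the plan says.** The supplied text is a synopsis, an abbreviation list and the Study Schedule.

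- **Timing of the VAS.** In the Study Schedule, "VAS for tooth sensitivity" is marked at visit 2 and blank at visit 3. It is marked for everyone at visits 4 (7-10 days) and 5 (6 months). At visits 6 to 9 it is restricted to participants with postoperative sensitivity.
- **Timing of allocation.** Visit 2 is the visit for "Preparation of tooth, impression and cementation of provisional restoration". Randomisation and "Use of Adhese Universal DC or Adhese Universal" are marked at visit 3 only.
- **Endpoint.** Synopsis, Outcome(s): "The primary endpoint of this RCT is the incidence rate of postoperative hypersensitivity". A separate schedule row, "Primary Variables", runs over visits 4 to 9. Synopsis, Measurements and procedures, adds that at the first recall "the study specific parameters will be evaluated according to the FDI Criteria ranging from 1 excellent to 5 clinically not acceptable". The text does not say which instrument defines the event, or whether sensitivity already present at visit 2 counts.
- **Analysis.** Synopsis, Statistical Considerations: "Non-parametric test (Mann-Whitney) between control and study group p=0.1 will be applied regarding the clinical parameters evaluated in this study". No covariate or change score is mentioned.
- **Use of the word baseline.** It is applied only to a visit after luting: "The baseline recall will take place 7-10 days after the insertion of the restoration".
- **Design.** Equivalence, 40 teeth per arm, up to two teeth from one participant.

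**The concern.** A sensitivity reading taken before allocation is a legitimate covariate and may predict later sensitivity. A Mann-Whitney test cannot use it. With 40 teeth per arm in an equivalence design, the width of the interval decides what can be concluded, so leaving out a predictor that is already collected may waste precision.

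A second, separate question is carry-over. Eligible teeth are vital with decay or a defective restoration, and no exclusion for prior sensitivity is stated. If such sensitivity persists to recall and is counted as postoperative, it adds the same background to both arms and shrinks the difference between them.

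**Working it through.** **1. The plan's own figure.** Forty teeth per arm cannot be reproduced: effect size, power, sidedness and margin are not given. One-sided 0.1, d = 0.5 and 80% power would give 39 per arm for a Mann-Whitney test, but d and power there are guesses.

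**2. Precision by formula.** Adjusting for a covariate with correlation r multiplies the variance by 1 - r², so the effective size per arm is 40/(1 - r²). All values of r are assumed.
- r = 0.2: 40/0.96 = 41.7
- r = 0.3: 40/0.91 = 44.0
- r = 0.5: 40/0.75 = 53.3
- r = 0.1: 40/0.99 = 40.4, and 40.4 × (1 - 1/77) = 39.9 after the lost degree of freedom, so no gain

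**3. Score outcomes by simulation.** 10,000 trials per setting, 40 per arm, two-sided 0.1. Visit 2 and recall are latent bivariate normal. VAS = round(25 × (z - 0.5)), clipped to 0-100, which gives 70% zeros and SD 10.3. The shift is 0.5 SD on the latent scale. The VAS scale and every rate are assumed.

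| Latent correlation | 0 | 0.3 | 0.5 | 0.7 |
|---|---|---|---|---|
| Observed Spearman | 0.01 | 0.20 | 0.36 | 0.54 |
| Mann-Whitney power | 59% | 59% | 59% | 59% |
| Rank ANCOVA power | 59% | 60% | 64% | 72% |
| Change-score power | 41% | 47% | 54% | 68% |
| Rank-ANCOVA variance ratio | 1.013 | 0.967 | 0.876 | 0.714 |
| 40/ratio | 39.5 | 41.4 | 45.7 | 56.0 |

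The ratios agree with step 2 applied to the Spearman values: 1 - 0.20² = 0.960, 1 - 0.36² = 0.870, 1 - 0.54² = 0.708. A repeat simulation gave about 60% unadjusted against 60 / 60 / 65 / 73%. Type I error was 9.4% to 10.2%.

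- *FDI-type 1-5 score, same covariate:* 59% becomes 58 / 59 / 63 / 71%.
- *Equivalence on mean VAS, arms truly equal, assumed margins:* at 5 units, 41% becomes 40 / 44 / 52 / 69%; at 7.5 units, 87% becomes 86 / 89 / 92 / 97%.
- *Two teeth per participant* (assumed 20 participants with two teeth and 40 with one, within-participant correlation 0.3), at correlations 0.3 / 0.5 / 0.7: clustered rank ANCOVA 59 / 63 / 73% against 58 / 58 / 61% unadjusted if teeth are randomised; 59 / 60 / 69% against 57 / 55 / 54% if participants are.

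**4. The primary endpoint, incidence.** Assumed 5% against 20%, two-sided 0.1. Exact Mann-Whitney power is 68%. Firth logistic regression with the covariate gives 64 / 66 / 68 / 76% at the same four correlations. The difference from the planned test is therefore -4, -2, 0 and +8 points.

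**5. Carry-over.** Let q be the share of teeth with persisting visit-2 sensitivity that is counted. The observed rate is q + (1 - q)p, so the difference is (1 - q)(p₂ - p₁). For assumed new-onset rates of 5% and 25%:
- q = 0: difference 20 points, power 81.5%
- q = 0.1: 14.5% against 32.5%, 18 points, 60.2%
- q = 0.2: 24% against 40%, 16 points, 45.5%

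Much of that loss is variance. For 5% against 20% with q = 0.15, the rates are 19.25% and 32%, a difference of 12.75 points. Non-significance rises from 32% to 63%. Raising the rates but keeping the 15-point difference (19.25% against 34.25%) already gives 54.6%. So about 23 of the 31 points are variance and 8 are dilution.

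**6. Direction of equivalence error.** Take a true new-onset difference equal to the margin and declare equivalence if the 90% Wald interval lies inside it. At q = 0 / 0.1 / 0.2 / 0.3, false equivalence is 6.7 / 2.5 / 0.2 / 0.0% for a 15-point margin and 6.2 / 7.2 / 7.6 / 5.4% for 20 points. There is no consistent direction.

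**The case against.** The strongest reply is that the declared primary endpoint is incidence, and there the planned test matches or beats the adjusted one up to a correlation of about 0.5. That stands, and it confines the recommendation to scores. Even for scores, the gain at correlations of 0 to 0.3 is 0 to 1 point. The schedule does not say whether the visit-2 reading is taken before or after preparation, so a low correlation is possible.

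Four stronger readings are tempting, and the documents support none of them.

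- *The unadjusted comparison is biased.* Randomisation follows visit 2, so there is no systematic confounding. Chance imbalance in prior sensitivity is not a defect, because the test's error rate already covers it.
- *Adjustment repairs carry-over.* It does not; that depends on the event definition. Incidence of postoperative sensitivity can also be read as new onset only, in which case nothing is diluted.
- *Counting earlier sensitivity makes false equivalence more likely.* Step 6 shows no fixed direction.
- *The plan never uses the visit-2 VAS.* That can be said only of the supplied pages. The abbreviation list includes terms, such as ITT, that those pages do not use, so fuller sections may exist.

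**Conclusion.** The point holds as an efficiency suggestion for score outcomes. The visit-2 VAS precedes allocation, and the one stated analysis does not use it. Adjustment is worth roughly 0 to 13 power points for a 0.5 SD shift over correlations of 0 to 0.7, or about 0, 1, 5-6 and 16 extra teeth per arm. All of this rests on correlations, distributions and effect sizes that the documents do not give.

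A VAS-score comparison in all participants is possible only at visits 4 and 5, since later VAS collection is limited to symptomatic participants.

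For incidence there is no case for replacing the unadjusted comparison. Carry-over is conditional on an event rule that the text does not state. This ranks below the missing margin and sample-size inputs.

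**What to change.** 1. For between-arm comparisons of sensitivity scores (VAS at visits 4 and 5, and any FDI sensitivity score), prespecify the visit-2 VAS as a covariate, not a change score. Use rank ANCOVA or a proportional-odds model, with standard errors clustered on participant.
2. Call it *visit-2 VAS*, because the synopsis uses *baseline* for the recall after luting. State whether it is recorded before or after preparation.
3. For incidence, keep the unadjusted comparison as the main analysis. Report a model with the visit-2 VAS as its one covariate only as a sensitivity analysis.
4. State whether sensitivity already present at visit 2 counts as an event. Report sensitivity new since visit 2 as a supporting analysis, with its margin set on that scale. For illustration, 15% background turns a 15-point difference into 15 × 0.85 = 12.75 points.

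**Cost.** No new data are needed. The covariate takes one analysis sentence, fixed before the arms are compared, and about 0 to 1 power point on scores if the correlation is zero. The loss of up to about 4 points on incidence is avoided by item 3.
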